Location: This study will take place at Duke Gynecology outpatient clinic, a hospital based clinic within the Duke system. This clinic operates 4 days per week (Tuesday through Friday) with a clinical volume of 1-4 procedures. Patients have their procedures with oral sedation and local anesthesia in the form of a paracervical block using lidocaine.

Approximately 220 women are have procedures under local anesthesia each year, with 2/3 of those patients being less than 8 weeks gestational age. Based on the patient volume, we do not anticipate any difficulty in recruiting patients to complete this study within the timeline presented. At this clinic, there are 3 providers whom have slightly different practices and protocols. Misoprostol for cervical preparation is used 2-3 hours prior starting procedures for cases at 12 to 14 weeks per provider preference.

Duke University School of Medicine, Department of Gynecology and Obstetrics at Duke University, where the study PI and coordination is based, has a strong clinical tradition, with its diverse patient population, the department have augmented expertise and experience across the discipline and provide a continuum of research opportunities in basic biomedical, translational, clinical and epidemiological research. This study will benefit from the existing research infrastructure at Duke for recruitment and enrollment.

Participant Selection:

A total of 96 women will be recruited and enrolled.

Inclusion and Exclusion Criteria

Inclusion criteria include:

- Women >=18 years-old
- Presenting for a surgical abortion
- No contraindication to outpatient abortion
- No contraindication to gabapentin
- Fluency in English and able to provide informed consent

Exclusion criteria include:

- Allergy, sensitivity or contraindication to gabapentin
- Severe renal disease, previously identified creatinine clearance of less than 30.
- Currently using gabapentin or pregabalin

Although patients on any chronic pain medications or with pre-existing pain conditions or history of alcohol or drug use may have a different metabolism or effect of the drugs, these women will not be excluded. Rather, data will be collected on these factors to evaluate the impact of these factors on study outcomes.

Description of the drugs and devices to be studied:

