Randomization to study method will occur after completion of all intake forms and consent, immediately before the pill is to be taken, thus reducing the possibility of withdrawal after randomization. Primary outcome measures and most secondary outcome measures will be assessed immediately before, during or after the abortion procedure, thus any loss to follow-up will be limited to those who consent to, but change their mind while waiting for their procedure. Based on current clinical practice at this clinic, withdrawal after consent is extremely rare. Our secondary outcomes assessed post-operatively after discharge will be collected via the phone. We will maximize completion of these assessments through the following steps: participants will be told beforehand about the telephone contact following the procedure, a cellular telephone number will be collected and tested at the clinic, a secondary phone number and email will be collected as a backup, participants will be given a contact number for the study coordinator should they have any challenges with receiving a phone calls, and participants will receive an additional \$10 sent to their gift-card following the completion of their phone assessment.

Data Collection/Outcome measurements:

Outcome measures and baseline variables are described in Table 1.

Primary study outcome

Our primary outcome measure will be pain score using an 100-mm visual analog scale (VAS) measured 5 minutes after removal of the speculum.

Secondary Outcomes:

We will also be measuring pain on the 100-mm VAS preoperatively immediately prior to the procedure, after the procedure, 10 minutes and 30 minutes following the procedure and at discharge. Nausea, using a VAS, and vomiting will be assessed preoperatively immediately prior to the procedure and post operatively at 10 minutes, 30 minutes and at discharge. Anxiety prior to the procedure will be measured using the preoperative state trait anxiety inventory. Side effects will be assessed using a checklist prior to discharge. We will also be contacting participants on post-operative day 1 to assess pain, nausea, vomiting, side effects and general satisfaction with the procedure (on a 5-point scale). The quantity and type of medications used perioperatively and post-operatively including medications used at home in the 24 hours post-operatively will be abstracted from the clinical record and assessed on the phone.

Baseline Characteristics and covariates:

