We will collect baseline demographics, medical history (gravidity, parity, prior abortions (medical and surgical), gestational age, drug and alcohol use, psychiatric or sexual assault history), medications used at home and given at the clinic preoperatively, indication for procedure (personal/social, fetal or maternal health)).

Study Size and Power:

We will enroll a total of 96 women. Assuming a standard deviation of 26 mm on the 100-mm visual analog scale (VAS), based on prior studies, this will provide us with an 80% power, using a p-value of 0.05, to detect a 15 point difference in pain among all participants. A difference of 15-20 mm has been assessed to be clinically meaningful in prior studies. Given that our primary outcome will be measured immediately after the procedure, our loss to follow-up will be minimal. A 100-mm pain visual analog scale has been shown to be useful for the evaluation of pain in prior pain abortion research [5, 6] with a mean standard deviation in previous studies of approximately 26 mm [5]. We are assuming no loss-to-follow-up as our primary outcome will be measured at the time of the procedure.

Data Management and Analysis

Data Management:

Prior to study initiation, a database will be developed using a web-based password-protected relational database (REDCap). All data will be collected will be recorded on clinical research forms (CRFs) and entered into the database at the end of each day. All CRF source documents will be filed and stored for future reference. See monitoring and oversight section below for further details on procedures and protections.

Analytic Plan:

We will compare groups on the primary continuous outcome measure (pain score on 11-point VAS) using T-tests. Chi-square and T-tests will be used to evaluate secondary outcomes for categorical and continuous variables, respectively. Baseline characteristics will be evaluated for potential interaction or confounding with primary and secondary outcomes.

Upon study completion at each site for the prospective meta-analysis, data from each site will contribute to the final meta-analysis using criteria outlined in the Cochrane Handbook for Systematic Reviews of Interventions. Site RCT publications will mention contribution to this PMA. Subgroup analyses will address gabapentin adjunct to local anesthesia and moderate sedation, as well as by specified population characteristics and gestational age.

Ethical Concerns

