2. Opiate Pain medication (including oxycodone, Percocet, oxycontin)	 ₀ NO  ₁ YES	 ₀ NO  ₁ YES	 ₁	 ₂	 ₃	Type: _____
3. Other pain medication	 ₀ NO  ₁ YES	 ₀ NO  ₁ YES	 ₁	 ₂	 ₃	Type: _____

HEALTH HISTORY

11. Have you ever been pregnant before (prompt: regardless of outcome)?

₀ NO ₁ YES → Answer questions a-e below

- a) How many times? _____
- b) Number of miscarriages or ectopic pregnancies _____
- c) Number of C-sections? _____
- d) Number of vaginal deliveries? _____
- e) Number of abortions? _____ (if 0 → 12)
- f) Number of medical abortions: _____
- g) Number of surgical abortions: _____
- h) Number under local anesthesia: _____

12. Now I will ask you a couple questions about your medical history

Do you have any of the following conditions			Follow-up questions if YES
1	Anxiety	 NO  YES	b. Do you take medication for it?  NO  YES c. Type of medication
2	Depression	 NO  YES	b. Do you take medication for it?  NO  YES c. Type of medication
3	Other psychiatric condition (such as bipolar, schizophrenia, PTSD)	 NO  YES	b. Other condition _____ c. Do you take medication for it?  NO  YES d. Type of medication

13. Have you ever been sexually or physically assaulted?

- NO
- YES, Sexually Assaulted
- YES, Physically Assaulted
- YES, Both sexually and physically assaulted

From Chart Abstraction:

Gestational Age: _____

Height: _____

Weight: _____

Anesthetic Regimen: ₁ LOCAL ₂ IV Moderate Sedation ₃ Deep Sedation

Medications Used:

Time of speculum placement: : AM/PM

Time of speculum removal: : AM/PM

Procedural Complications?

\square_0 NO \square_1 YES: Description:

Preop Assessment

Time: ___ ___ : ___ ___ AM/PM

For these questions we are going to ask you to make a hash mark on a line.

For example, let's say you are asked how much you like Oreo cookies:

How much do you like Oreo cookies? (make a hash mark on the line)

very

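### The plan says its three providers practise slightly differently but does not list the operator as a recorded, stratifying or adjustment variable; recording it and adjusting for it would be a minor gain in precision

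*Combined protocol and SAP*

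**What the plan says.** The Location section describes one clinic and says of its staff: "At this clinic, there are 3 providers whom have slightly different practices and protocols". It gives one example of practice that varies: "Misoprostol for cervical preparation is used 2-3 hours prior starting procedures for cases at 12 to 14 weeks per provider preference". The anaesthetic approach is described once, for the clinic's patients in general: "Patients have their procedures with oral sedation and local anesthesia in the form of a paracervical block using lidocaine". Both study arms receive usual perioperative pain management plus the study pill.

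Randomisation is 1:1 in variable blocks of 8 and 10, and no stratification is stated. The Analytic Plan compares the primary outcome, pain 5 minutes after speculum removal, by t-test. It adds that baseline characteristics will be examined for interaction or confounding, but names no model.

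The list under Baseline Characteristics and covariates covers demographics, medical and obstetric history, gestational age and substance use, and closes with "medications used at home and given at the clinic preoperatively, indication for procedure". Provider is not on it. The chart abstraction block of the Draft Questionnaire has gestational age, height, weight, regimen, medications, speculum times and complications, but no operator. The name field at the top of the questionnaire is for the interviewer. Table 1, which the protocol cites for outcome measures and baseline variables, is not in the available text.

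**The concern.** Pain shortly after an aspiration may well depend on who did the procedure and on how that person prepares the patient. The plan itself says that practice varies by provider, and background care in both arms follows usual practice. An unadjusted t-test leaves any variation between operators in the error term. The planned look at baseline characteristics cannot cover a variable that is not among those collected, so a chance imbalance of operators between arms would not be examined either. The sample size has little slack: 96 women give almost exactly 80% power, with no loss assumed. A cheap source of precision is therefore worth having.

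**Working it through.** **Inputs from Study Size and Power:** SD 26 mm, difference 15 mm, 80% power, alpha 0.05, 96 women (48 per arm). From Location: three providers. The documents give no caseload per provider and no provider effect on pain. Both are assumed below.

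**The plan's own figure.** Two-sided, n per arm = 2 × (1.960 + 0.842)² × 26² / 15² = 47.2, rounded up to 48, so 96 in total. The stated size reproduces. Power at 48 per arm is 0.807 by the normal approximation and 0.799 by the t distribution. One-sided testing would need only 38 per arm, so the plan is evidently two-sided.

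**Gain from adjustment, with 26 mm as the total SD.** Assume three equal caseloads of 32 and provider mean pain of −d, 0 and +d mm around the middle provider. The between-provider variance is 2d²/3, its share of 26² = 676 is (2d²/3)/676, and the residual SD after adjustment is 26 × √(1 − share). Power is for the two-sided t-test, 48 per arm, 15 mm.

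| d (mm) | Between-provider variance | Share of 676 | Residual SD (mm) | Power |
|---|---|---|---|---|
| none | 0 | 0% | 26.0 | 0.80 |
| 5 | 16.7 | 2.5% | 25.7 | 0.81 |
| 10 | 66.7 | 9.9% | 24.7 | 0.84 |
| 15 | 150 | 22.2% | 22.9 | 0.89 |

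Using 92 degrees of freedom rather than 94, for the two operator terms, does not change these rounded values.

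**If 26 mm is instead the within-provider SD.** The documents do not say whether the SD from prior studies includes variation between operators. If it does not, the planned t-test falls short of its stated power. For provider shares of 5%, 10% and 20% of total variance, unadjusted power is 0.787, 0.765 and 0.715 (normal approximation).

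**Bias and type I error.** A simulation used 8,000 trials per scenario, 96 women, three equally busy providers, unstratified blocks of 8 and 10, and a within-provider SD of 26 mm. Adjacent providers were 0, 10 or 20 mm apart. The mean error of the unadjusted estimate was under 0.1 mm and its type I error was 0.051 to 0.052, matching the adjusted analysis. Unadjusted power was 0.79, 0.75 and 0.65, against 0.78, 0.79 and 0.79 adjusted.

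**Chance imbalance.** Treat allocation as unrestricted within provider, so that the number on gabapentin among one provider's 32 patients is hypergeometric (96, 48, 32). A given provider then splits 20:12 or worse with probability 0.129. If that provider's patients score 10 mm higher, the difference between arms shifts by 10 × (20 − 12)/48 = 1.7 mm. The standard error of the unadjusted difference is 26 × √(2/48) = 5.3 mm, so the shift is about 0.3 of a standard error.

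**The case against.** The strongest reply is that validity is not at stake. Blinded 1:1 randomisation prevents systematic confounding by operator, and the t-test's standard error already allows for chance imbalance. That stands: the 1.7 mm shift is one unlucky draw, not a bias.

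The second reply is that the effect is probably small. The protocol calls the differences slight, and its one example applies only at 12 to 14 weeks, in a clinic where about two thirds of local-anaesthesia patients are under 8 weeks. Adjacent gaps of 10 or 15 mm put the extreme providers 20 or 30 mm apart, more than the 15 mm target difference. This stands too, and it points to the first row of gains in the table.

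Third, a reader might infer that operator differences can never be removed from the data. The documents do not support that. The form is labelled a draft, chart abstraction is already planned, the operator can probably be found in the clinical record, and Table 1 could not be checked. The gap is an unlisted variable, not lost information.

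Fourth, the regimen item, "Anesthetic Regimen: ₁ LOCAL ₂ IV Moderate Sedation ₃ Deep Sedation", has no oral-sedation box, and a reader might take this as further evidence of hidden operator differences, or think that the site's oral sedation would be concealed from the meta-analysis. Neither follows. Oral sedation is described as the clinic's general practice, and the form has an open entry, "Medications Used". Nor does that single open entry show that drugs given before and after the procedure cannot be told apart. The outcomes section takes "The quantity and type of medications used perioperatively and post-operatively" from the clinical record and by telephone, the covariate list has preoperative clinic medications as its own item, and the 24-hour call asks about medication taken since leaving.

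**Conclusion.** The point holds as a minor matter of precision and completeness. The plan identifies a source of variation, then neither lists it among the variables to record nor uses it in the design or the analysis. It would be wrong to infer that the comparison of gabapentin with placebo is biased or that its type I error is inflated; randomisation protects both. With 26 mm as the total SD and equal caseloads, adjustment adds about 1, 4 or 9 percentage points of power for adjacent provider gaps of 5, 10 or 15 mm, most plausibly near the low end. The loss would matter more only if 26 mm is a within-provider SD and providers differ widely. The documents establish neither. The conclusion also depends on the visible lists, since Table 1 might name the operator.

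**What to change.** Add a coded operator field (A/B/C) to the chart abstraction block of the Draft Questionnaire and to the list under Baseline Characteristics and covariates. In the Analytic Plan, prespecify before unblinding a linear model of 5-minute pain on treatment plus operator as a fixed effect, alongside or in place of the t-test, and state which of the two is primary. Tabulate operator by arm with the other baseline characteristics.

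The cost is one more item from a chart that is already being abstracted, and two degrees of freedom in the model. If operators turn out not to differ, almost no power is lost (0.799 either way by the t calculation). Patient care, randomisation and sample size need not change.

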Pain control during and after abortion is a Society of Family Planning priority. Pain management regimens for surgical abortion can rely on local anesthetic, oral analgesics, moderate sedation, deep sedation, or a combination of approaches. While several recent studies have attempted to reduce pain with adding supplemental medications or therapies, such as nonsteroidal anti-inflammatory drugs, narcotics, anxiolytics, misoprostol, nitrous oxide, music, most studies have failed to improve pain scores. As optimal pain management has not been established, many women continuing to report moderate to severe pain during and after the procedure [1].

We propose a novel regimen of oral gabapentin administered prior to usual pain management regimens for surgical abortion. Gabapentin is used to treat neuropathic and chronic pain. Mechanism of action may include calcium channel blockade and modulation of nociceptive neurotransmitters. Clinical trials support use of perioperative gabapentin to reduce post-surgical pain in a variety of clinical settings[2]. Gabapentin is well-tolerated and inexpensive, with mild, if any, side effects. [3] In a systematic review of 22 randomized controlled trials (RCT) of multiple surgical procedures including ambulatory nasal surgery, orthopedic procedures and laparotomy, a single preoperative dose of gabapentin significantly reduced 24-hour opioid consumption[3]. Perioperative gabapentin before hysterectomy showed reduced pain scores, nausea and vomiting [4, 5] A randomized trial in the setting of cesarean showed improved pain scores and decreased pain requirements with a 600 mg dose of preoperative gabapentin [5]. Its use in the setting of abortion has never been evaluated.

We hypothesize that adding gabapentin preoperatively to current pain management regimens will reduce pain associated with surgical abortion. Additionally, we hypothesize that preoperative gabapentin will reduce perioperative nausea, vomiting and anxiety with few adverse effects.

Primary Aim: To evaluate the impact of adjunctive preoperative gabapentin on perioperative pain during uterine aspiration <15 weeks of gestation for abortion and pregnancy loss management compared to usual pain control regimens

Secondary Aims

- To evaluate the impact of preoperative gabapentin on:
 - perioperative nausea and vomiting
 - preoperative anxiety
 - use of pain medications and anti-emetics post-operatively

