opioid consumption [3]. In the setting of obstetrics and gynecology, evidence supports perioperative gabapentin before hysterectomy to reduce pain scores, nausea, and vomiting [4, 5]. Preoperative gabapentin prior to cesarean section improved pain scores at 24 hours with less need for post-operative analgesia compared to placebo [5]. In an outpatient setting similar to abortion surgery, perioperative gabapentin have been shown to decrease post-operative opioid consumption and anxiety for minor orthopedic procedures and hemorrhoidectomy [13, 14].

Innovation in pain control and reduction of anxiety, nausea and vomiting using a low cost, well-tolerated intervention could impact hundreds of thousands of women each year with potential implications for other common outpatient gynecologic procedures. We propose a novel use of oral gabapentin administered in conjunction with usual pain management regimens for surgical abortion. *Use of gabapentin in the setting of uterine aspiration has never been evaluated; however it is used routinely and successfully in several similar surgical settings as an adjunct to pain management regimens.* It is generally well-tolerated and inexpensive, with minimal side effects and few contraindications [3]. If effective, this simple adjunct to current pain regimens could expand options for the management of women worldwide undergoing surgical abortions. Other secondary outcomes such as nausea, vomiting and anxiety influence a woman's ability to return to her normal baseline level of activity and her experience of abortion in general. Our prospective meta-analysis (PMA) design will allow us to simultaneously evaluate the impact of gabapentin among different gestational ages and combined with different anesthesia regimens to determine if there is utility of this easy to use, safe adjunct therapy in differing abortion care settings.

Study Design and Methodology

Study Design: This is a randomized controlled double-blind placebo-controlled trial evaluating the impact of gabapentin given preoperatively on perioperative pain scores for women receiving uterine aspiration between 6 and 14+6 weeks gestation. This study will be a trial included in a prospective meta-analysis evaluating the use of gabapentin on perioperative pain in the abortion setting.

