Women undergoing a procedure who meet study inclusion criteria and complete informed consent will be eligible for participation. *Randomization* will be done using computer-generated random numbers (randomization.com) in variable blocks of 8 and 10. *Allocation* concealment will be maintained by identically labeled sealed sequentially numbered opaque pill containers. Gabapentin and placebo tablets will be indistinguishable by appearance, thus maintaining blinding for participants and assessors. To maintain double *blinding* for both investigators and participants, an individual not associated with study conduct will create the randomization sequence and allocation containers. The randomization assignments will only be revealed at the point of data analysis or if an interim assessment is needed.

Enrollment:

After the final perioperative clearance, the individual will be randomized and receive their method allocated by the clinic nurse. The study staff will review the enrollment questionnaire that includes demographic questions. Following completion of the questionnaire, the participant will wait before moving to our procedure room (this will occur approximately 1-2 hour after nursing review and receipt of the study intervention). Prior to initiating the procedure, study staff will administer the preoperative questions. The physician will then complete the uterine aspiration while the study staff remains outside of the operative room. Immediately following the procedure, the study staff will then administer the immediate post-operative questions and follow the participant to the recovery room to complete the remaining questions assessed at 5 minutes, 10 minutes, 30 minutes and at discharge. When the discharge questions are complete, the

participant will receive a \$20 gift card and instructed to expect a follow-up call the following day.

Follow-up:

On the day following the procedure (approximately 24 hours after the procedure), study staff will call the participant to complete the follow-up questions. On completion of the questions, an additional \$10 will be transferred to the gift card.

Withdrawals, losses and deviations:

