The benefits of this research extend to potentially leading to improvements in the pain management procedures provided at the facility. Moreover, the results could potentially impact individuals globally as we aim to better address pain management in the setting of outpatient abortions. Participants will receive a \$30 compensation for study participation, \$20 at the clinic and \$10 following completion of the telephone follow-up.

Importance of the knowledge gained

The current study could help us to better manage perioperative pain during an abortion. Inclusion in the PMA, will provide robust information to address the inclusion of gabapentin in

different settings to further elucidate any benefit of this intervention. Study findings will be disseminated further via abstracts submitted to scientific meetings and manuscripts submitted to peer-reviewed journals in addition to a Cochrane Review. Benefit proven in the setting of outpatient abortion care would give precedence for exploring the use of gabapentin for other outpatient procedures.

Monitoring and Oversight

Site monitoring

Site monitoring may be performed by the Duke University's IRB and Office of Research Compliance, OHRP, FDA, or other government regulatory authorities. Clinical research site monitoring may include the review of the individual participant records, including consent forms, CRFs, supporting data, and medical records (physicians' progress notes, nurses' notes, individuals' hospital charts) to ensure protection of study participants, compliance with the protocol, and accuracy and completeness of records. The monitors may also inspect sites' regulatory files to ensure that regulatory requirements are being followed. The investigator will make study documents (e.g., consent forms, CRFs) and pertinent clinic records readily available for inspection.

Data quality assurance and protection

There will be study protocol and procedure training for all study staff prior to beginning of the study. A standard operations manual will be available to staff to refer to for operational details in running the study.

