Appendix A

Clinic Recruitment Procedures

Recruitment script *“We would like to invite you to participate in a study that is looking at a medication called Gabapentin and how it may affect the pain you experience during your abortion procedure. This medication is very safe and has been used in many other surgical settings however has not been studied in the abortion setting. Your participation is completely voluntary and will not influence the care you receive at the clinic. During this study, you will be given the medication or a placebo, which is a pill that does not contain any medication, 1-2 hours prior to your procedure. Neither you nor the research or clinic staff will know whether you received the Gabapentin or not. We will be looking at your experience during and after the procedure, which will include your experience of discomfort, nausea, vomiting or any side effects. In addition to your visit today, we will contact you tomorrow to briefly ask you some questions. The study procedures today will be completed while you are waiting for your procedure and after your procedure. It should not delay your time at the clinic. You will be reimbursed \$20 for your time today and receive an additional \$10 after completing the phone call tomorrow. If you are interested in participating, we will give you a consent form to read and we can go through the study in detail with you. Again, whether or not you choose to be in the study will not affect your care at the Clinic. Are you interested in seeing if you are eligible?”*

Eligibility checklist:

- 1) What is your age? ____ (must be **18 years-old or older** to be eligible)
- 2) Are you here today for a surgical abortion or medication abortion or another procedure (must be **surgical abortion**)
 - 1) Medical
 - 2) Surgical abortion
 - 3) Other _____
- 3) Are you fluent in English and able to provide informed consent (must be **Yes**)
 - 1) Yes
 - 2) No
- 4) Do you have an allergy, sensitivity or other reason why you can not receive Gabapentin (must be **No**)
 - 1) Yes
 - 2) No
- 5) Do you have any renal disease (must be **No**)
 - 1) Yes
 - 2) No
- 6) Are you currently using gabapentin or pregabalin (must be **No**)
 - 1) Yes
 - 2) No

Duke Consent

You Are Being Asked to Be in a Research Study

What Is a Research Study?

The main purpose of research studies is to gain knowledge. This knowledge may be used to help others. Research studies are not intended to benefit you directly, though some might.

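### Does keeping study staff outside the procedure room leave the aim on pain during aspiration without a usable outcome?

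*Combined protocol and SAP*

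**What the plan says.** The Primary Aim concerns "perioperative pain during uterine aspiration <15 weeks of gestation". The Study Design paragraph is broader and refers to "perioperative pain scores for women receiving uterine aspiration". The section on the importance of the knowledge gained speaks of helping to "better manage perioperative pain during an abortion". The recruitment script in Appendix A tells women that the study looks at gabapentin and "how it may affect the pain you experience during your abortion procedure"; further on, it says that the experience after the procedure is of interest too.

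The primary outcome is a 100-mm VAS pain score 5 minutes after the speculum is removed. The secondary pain scores are taken "preoperatively immediately prior to the procedure, after the procedure, 10 minutes and 30 minutes following the procedure and at discharge", with a further telephone assessment on day 1. The same part of the protocol states: "Outcome measures and baseline variables are described in Table 1".

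On conduct, Enrollment says: "The physician will then complete the uterine aspiration while the study staff remains outside of the operative room". It continues: "Immediately following the procedure, the study staff will then administer the immediate post-operative questions". Staff then go with the participant to recovery for the 5-, 10- and 30-minute and discharge questions.

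The Draft Questionnaire has an intraoperative block for local anesthesia, the regimen described for this clinic. It holds four VAS lines (speculum insertion, block injection, dilation, suction) and three entries marked for study staff that record when the block, dilation and suction ended, in minutes and seconds from speculum insertion. The 5-, 10- and 30-minute and discharge forms each carry a line for the worst pain so far that day and a line for current pain.

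**The concern.** Two things look wrong. First, the aim and the script point to pain during the procedure, while the outcomes named in the prose sit on either side of it. Current pain 5 minutes after the speculum comes out cannot by itself show whether the aspiration hurt less. The form does collect measures closer to that question, but the prose does not name them as outcomes, and Enrollment does not say when the intraoperative lines are completed. If no such measure is fixed in advance, a later claim about suction pain or worst pain could be challenged as chosen after the data were seen.

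Second, staff who are outside the room cannot time the end of the block, the dilation or the suction, and no relay from inside is described. At stake would be the credibility of any statement about intraoperative pain and the quality of three form fields.

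**Working it through.** **1. The plan's own figure.** Study Size and Power gives SD 26 mm, a difference of 15, a p-value of 0.05 (taken as two-sided), 80% power and 96 women; Recruitment gives equal allocation.

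- Per arm: n = 2 × (1.960 + 0.842)² × 26² / 15² = 2 × 7.85 × 676 / 225 ≈ 47.2, rounded up to 48, so 96 in total. This matches the plan.
- Power at 48 per arm: 15 / (26 × √(2/48)) = 15 / 5.307 = 2.826; 2.826 − 1.960 = 0.866; Φ(0.866) = 80.7%. The t-distribution gives 79.9%.

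Neither the intraoperative lines nor the three timings enter this calculation.

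**2. Timing, side by side.**

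- During aspiration: staff are outside the room. Only the three elapsed-time entries need someone inside.
- Straight after: staff ask the immediate post-operative questions. The four intraoperative lines ask what pain the participant had, in the past tense, and their numbering (1 to 4) runs on to item 5, current pain on speculum removal. Recall at this contact fits both Enrollment and the form. The separate heading and the time field on item 1 leave some doubt, but neither rules this out.
- At 5 minutes: staff are present and the primary score is taken. It is read here as the current-pain line, item 2 of that form.

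So the pain lines can be collected as Enrollment is written. The direct conflict is confined to the three timings. Speculum placement and removal times are recorded separately under chart abstraction, and no outcome or analysis in the prose uses the intermediate times.

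**3. Room for selection.** By the 5-minute visit, 4 intraoperative lines + 1 worst-pain line = 5 candidates. With no true effect, the chance that at least one reaches p < 0.05 is:

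- perfectly correlated: 5%;
- independent: 1 − 0.95⁵ = 1 − 0.774 = 22.6%.

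The documents give no correlation. These are overlapping ratings by the same woman within one visit, so independence is implausible. The calculation also supposes that all five are tested and that Table 1 names none of them. No section plans those five tests.

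**4. Burden before the primary score.** If the intraoperative lines are asked with item 5, the lines before 5-minute current pain number 4 + 1 + 1 (5-minute worst pain) = 6. Without them there are 1 + 1 = 2. Making a recalled line a formal outcome would commit the trial to four more lines just ahead of the time-critical primary score.

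**The case for a change.** The best case for a change comes from the protocol itself. Its background treats pain during and pain after the procedure as separable: it reports that general anesthesia does better on the first without being superior to moderate sedation on the second. A post-procedure score therefore cannot stand in for aspiration pain. Problems Anticipated also says that study operation will not depend on clinic staff, which makes an unstated relay of timings harder to assume. Naming one measure in advance would take a sentence.

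Part of this stands. The 5-minute score alone does not answer for the aspiration, and the three timings cannot be squared with Enrollment as written.

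The rest is weaker. The aim is perioperative pain, and a score taken 5 minutes after the speculum comes out lies within that period. The section on withdrawals and losses says that most outcomes are assessed before, during or after the procedure. It names no intraoperative measure, but it shows that assessment during the procedure was contemplated. Since outcome measures are referred to Table 1, silence in the prose does not establish a gap. When to hand over past-tense items is the kind of detail that the standard operations manual mentioned in the protocol exists to hold.

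Nor is there an obvious better outcome to name. The intraoperative lines are for local anesthesia only, so they would not serve the planned meta-analysis across local anesthesia and moderate sedation. Worst pain so far covers the whole day, not just the procedure.

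**Conclusion.** No change to the plan follows. The three staff timings are a clerical conflict on a form headed as a draft. They can be dropped or given to someone in the room when the form is finalised, with no effect on any stated outcome. The unstated moment for the four recalled pain lines is a gap that staff can fill sensibly at the contact already scheduled. Whether to make one of those lines a formal secondary outcome is a fair trade-off against the load on the participant just before the primary score.

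The primary outcome, the 96 participants and the t-test are unaffected: the effect on the primary analysis is nil. If Table 1 names no measure of pain during the procedure, the normal convention covers the remaining risk: a result on an unnamed measure is reported as exploratory, and the trial's claim rests on pain 5 minutes after speculum removal. The 22.6% figure should carry no weight, because it needs independence and five tests that are not planned.

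This rests on reading the primary score as the 5-minute current-pain line and the past-tense items as recall items. Table 1 was not available to check.
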